#### Stopping rule

Power estimates based on simulations indicate that a total of 60 participants will be needed to detect the expected effects. Because we are interested in outcomes that are assessed one year after treatment, and there is minimal risk to treatment participation, we will not stop study recruitment until we have reached our recruitment goal.

#### Variables

##### Manipulated variables

See attached file for details.

- [Manipulate Variables.pdf](#)

##### Measured variables

See attached file for details.

- [Measured variables.pdf](#)

##### Indices

No indices of any type will be calculated. Rather we will use all of the scores described in the measures section for the proposed analyses.

*No files selected*

#### Design Plan

##### Study type

Experiment - A researcher randomly assigns treatments to study subjects, this includes field or lab experiments. This is also known as an intervention experiment and includes randomized controlled trials.

##### Blinding

- For studies that involve human subjects, they will not know the treatment group to which they have been assigned.
- Research personnel who interact directly with the study subjects (either human or non-human subjects) will not be aware of the assigned treatments.

- Research personnel who analyze the data collected from the study are not aware of the treatment applied to any given group.

### Study design

The study is a three-group randomized design, with each participant being randomly assigned to one of three conditions. The design is mixed as there are both between participant (treatment condition) and within participant (word list) factors of interest. The factors will be counterbalanced to ensure that both word lists are represented in each treatment condition. Additional notes on blinding of research personnel who interact directly with subjects: The research assistant who administers the treatment cannot be blind to the treatment condition. They must know the treatment condition to correctly deliver it. This same research assistant collects during treatment because it would be cost prohibitive to send a second research assistant to every treatment to collect these data. Blinding of research personnel occurs in the following ways: (1) The research assistant (RA) administering pre- and post-treatment testing is blind to condition assignment to reduce bias. (2) All tests are scored by RAs who are blind to the treatment condition to reduce bias.

*No files selected*

### Randomization

Random assignment to the three treatment condition occurs at the participant level. Participants will also be randomly assigned to one of two treated word lists within each treatment condition.

## Analysis Plan

### Statistical models

Research Question 3.1: We will use a multi-level modeling approach for (a) learning during treatment (7 observations: pre-treatment, repeated readings 1-6); (b) post-treatment forgetting (5 observations: reading 6, immediate, 4-week, 8-week, 12-week post). We will examine definition and naming data separately, yielding four models: treatment definition, treatment naming, post-treatment definition, post-treatment naming. For each model, observations at each test (level 1) are available for each participant (level 2). The expected shape of the trajectories is not known so the analytic approach will use either linear growth modeling or latent basis modeling, depending on which is most appropriate. Participants are randomly assigned to treatment (low, mid, high testing), and treatment will be included in the model as a fixed factor at level 2. The dependent variable is number of words correct. This count variable will likely not fit a normal distribution, and thus, an appropriate link function, such as a Poisson distribution, will be used. The research aim is to detect

differences between treatment conditions, therefore all possible pairwise comparisons will be conducted rather than an omnibus test. The slope by treatment condition interaction will be the effect of interest in determining whether there is differential learning or forgetting across low, mid, high testing. While the focus of our analyses is on treated words, a similar modeling approach will be used to model any learning of control words during treatment. We expect relatively flat trajectories for control words in all three treatment conditions and this will allow for inferences to be made about the effect of treatment rather than development or maturation Research Question 3.2: We will add pre-treatment measures as covariates to the models used in RQ3.1 to examine the relationship between these covariates and (a) learning slopes during treatment and (b) forgetting slopes post-treatment. Recall that there are several skills relevant for learning (language, attention, working memory, episodic learning) and forgetting (treatment learning, decay) and that we have multiple measures to tap different aspects of each skill (see measured variables table). Likewise, we also will examine biological and environmental variables as predictors. Previous research has indicated that the test measures are moderately correlated at around  $r = .50$ . Since these measures are theoretically and mathematically distinct (which we will confirm via correlations), we will examine the effect of each of these predictors individually. We hypothesize that higher language, attention, working memory, and/or episodic learning scores will be associated with steeper slopes during treatment. Similarly, we hypothesize that better treatment learning and decay scores will be associated with smaller slopes, indicating less decline post-treatment. These hypotheses are consistent with theories of learning and forgetting. However, it is likely that not all of these covariates will be significantly related to performance. Research Question 3.3: We will classify responses at the end of treatment (learner vs. non-learner) and post-treatment (rememberer vs. forgetter). Then, earlier performance will be analyzed to determine when treatment and post-treatment outcomes can be predicted. This yields empirically based benchmarks for progress and an understanding of the stability of learning and forgetting over time. As with RQ 3.1 and 3.2, we will separate treatment and post-treatment data as well as definition and naming data. Within each dataset, we will classify each child as having a negative or positive outcome based on performance at the last point in the series (i.e., reading 6 for treatment, 12-month post for post-treatment). We will use the accuracy range for the untreated control words to determine the cut-offs for this classification. Then, we will select an appropriate cut-off score at each earlier point during treatment or post-treatment. Because we have decided that the cost of false positives is greater than that of false negatives (see progress report), we will select cutoffs that minimize false positives. At each test point, measures of sensitivity, specificity, and positive/negative likelihood ratios and predictive values will be calculated. We will then determine the earliest point when we can accurately predict treatment and post-treatment outcomes

*No files selected*

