### **Sampling Plan**

#### **Existing Data**

Registration prior to creation of data

Explanation of existing data

N/A -- Not using existing data

Data collection procedures

See attached file for details.

- [Data collection procedures.pdf](#)

Sample size

Sixty kindergarten children with DLD will participate. Children will be randomized to one of the 3 treatment manipulations (see manipulated variables) yielding 20 children per treatment condition. For each child definition and naming data will be collected for 30 treated words and 30 control words: 1 time pre-treatment, 6 times during treatment (repeated book readings 1-6), and 4 times post-treatment (immediate, 4-weeks, 8-weeks, and 12-weeks post-treatment).

Sample size rationale

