3.1. Power Analysis for Research Question 3.1. Monte Carlo studies were conducted using Mplus to determine power to detect treatment differences in slope across 7 (treatment) or 5 (retention) data points. Slope reliabilities of .6 and .8 were considered in the specification of the population parameters. Both linear growth models and latent basis models with nonlinear growth were examined given that the expected shape of the trajectories is uncertain. Intraclass Correlation Coefficients (ICCs) from our prior studies indicated that between 10% and 30% of the variance in word learning was between persons. Thus, ICCs of both .10 and .30 were used in the power analysis. We will have .80 power or greater to detect moderate slope differences ( $d = .5$ ) between two groups of 20 individuals in the treatment phase with 7 data points. In the post-treatment phase, with 5 data points, we will have .80 power to detect slightly larger slope differences ( $d = .6$ ). Attrition has been minimal (1.9%). Thus, we will recruit additional children, as needed, to replace any children who do not complete the study. We will check the assumptions used in our power analysis yearly and update target sample size to maintain power. 3.2. Power Analysis for Research Question 3.2. Additional Monte Carlo studies were conducted using the same software, intraclass correlation coefficients, and slope reliabilities as for RQ3.1. Prior research by the team has indicated that correlations between predictors and learning are in the range of .4 and .5. Power to detect the relationship between level two predictors of this magnitude and slopes added to the treatment model will range from .70 to .85. Power to detect the main effect of each covariate at the last treatment point will similarly range from .73 to .87. Although power appears sufficient with a sample size of 60, an alternative approach if power is insufficient is to loosen our criteria for statistical significance and search for “promising” key moderators. Promising key moderators would need further testing as the

development of this treatment moves forward but would inform our understanding of which children with DLD may benefit from the treatment, addressing the research question. 3.3 There is no specific power analysis for research question 3.3.

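### Optional precision gain: the RQ3.1 models pre-specify neither the randomised treated word list nor, in the treatment phase, a pre-treatment score, and one good score would be worth about 7–14% more children

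*Combined protocol and SAP*

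**What the plan says.** **RQ3.1 models (Statistical models).** Four growth models are planned: definition and naming, each in the treatment and post-treatment phases. The only between-child term named is condition: "treatment will be included in the model as a fixed factor at level 2". Inference is on the slope-by-condition interaction, and "all possible pairwise comparisons will be conducted rather than an omnibus test". The sample size section has 60 children, "yielding 20 children per treatment condition", so each contrast is 20 v 20.

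**Word list.** Under Randomization, "Participants will also be randomly assigned to one of two treated word lists within each treatment condition". Under Study design, "The factors will be counterbalanced to ensure that both word lists are represented in each treatment condition", and word list is called a factor of interest. No RQ3.1 model names it.

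**Pre-treatment scores.** The Sample size rationale for RQ3.2 reports that "correlations between predictors and learning are in the range of .4 and .5", and that power to relate such predictors to "slopes added to the treatment model will range from .70 to .85". The analysis section adds these scores to the RQ3.1 models only for RQ3.2, one at a time, to study the scores themselves. It expects that some of them will not be related to performance.

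**Pre-treatment word test.** It is already a response in the treatment-phase models: "learning during treatment (7 observations: pre-treatment, repeated readings 1-6". It therefore cannot also serve as the covariate.

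**Choice of fixed effects (Inference criteria).** Likelihood ratio tests on nested models decide which random and fixed effects are kept. Neither list nor any score is named there.

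**The concern.** A factor that is randomised within condition, and a baseline score expected to predict the outcome, are the two usual candidates for a pre-specified adjustment. Both are already collected here. If they explain between-child variation in slope and are left out, that variation stays in the error of each 20 v 20 contrast. If they enter only through likelihood-ratio selection, the model behind the main contrasts is chosen after outcomes are seen.

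Only precision is at stake, together with some protection against doubts about model selection. Because the contrast is on slope, an adjustment helps only if the term is also crossed with time; a main effect alone would leave the slope variance untouched.

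**Working it through.** **Inputs from the documents.** N = 60, 20 per condition; RQ3.2 slope power .70 to .85; predictor–learning correlation .4 to .5; slope reliability .6 and .8; correlation among measures about .50.

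**Assumptions.** No alpha is stated, so two-sided .05 is assumed, with .10 and .01 as a range. The approximation is linear, on per-child slopes.

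**1. The plan's own RQ3.2 power.** With observed r = stated r × √reliability, power = Φ(atanh(r)·√57 − 1.96).

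| stated r | reliability | observed r | power |
|---|---|---|---|
| .4 | .6 | .310 | .68 |
| .4 | .8 | .358 | .81 |
| .5 | .6 | .387 | .87 |
| .5 | .8 | .447 | .95 |

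The lower stated end is close (.68; .70 by noncentral F). The grid runs above the upper stated end. The Monte Carlo settings are not given, so the range is neither confirmed nor refuted. The rest works back from the stated power, which is the more cautious route.

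**2. Implied observed correlation.** r = tanh[(1.96 + z_power)/√57].
- Power .70: (1.96 + .524)/7.550 = .329, r = .318, r² = .101.
- Power .85: (1.96 + 1.036)/7.550 = .397, r = .377, r² = .142.

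**3. Gross gain, 1/(1 − r²).** 1.112 and 1.166, or 11% and 17%.

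**4. Net gain after fitting score and list.**
- Lists exactly balanced within condition (list is orthogonal to condition): multiply by 54/55, giving 1.092 and 1.145.
- Lists assigned by simple randomisation and not truly different: multiply by 54/56, giving 1.073 and 1.124.

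Simulation (20,000 runs, 3 × 20 children, score and list fitted) gave these variance ratios, unadjusted over adjusted. A repeat run agreed to about .01.

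| observed r | balanced lists | simple randomisation |
|---|---|---|
| 0 | 0.98 | 0.96 |
| .2 | 1.02 | 1.00 |
| .318 | 1.09 | 1.07 |
| .377 | 1.14 | 1.13 |

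The net gain is thus about 7–14%: 60 children act like about 64 (60 × 1.073) to 69 (60 × 1.145). A score with no predictive value costs 2–4%. Simulated type I error was .048–.053 with and without adjustment.

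**5. Sensitivity to alpha (balanced lists).** At .10, r = .280 and .341, net 7–11%. At .01, r = .389 and .445, net 16–22%. Replacing 54/55 by 54/56 for simple randomisation lowers these to about 5–9% and 14–20%.

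**6. What it does to power.** Φ[(z_base + 1.96)·√ratio − 1.96], for ratios 1.07 to 1.14: from .80 to .83–.85; from an assumed .50 to .53–.55; from an assumed .35 to .37–.39.

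**7. Word list.** The documents give no list effect. For an assumed gap of d slope SDs between lists, the unadjusted variance is inflated by 1 + d²/4. Under simple randomisation, multiply by 55/56 for the net ratio.
- d = 0.2: 1.01, net 0.99.
- d = 0.5: 1.06, net 1.04.
- d = 1.0: 1.25, net 1.23.

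**8. Why RQ3.2 needs its own base model.** If the chosen score stayed in, a second score correlated .50 with it would have partial r = (r − .5r)/√[(1 − r²)(.75)] = .194 and .235. Its power would be Φ(atanh(partial r)·√56 − 1.96) = .31 and .43, instead of .70 and .85.

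**The case against.** **The plan does not rule these terms out.** The likelihood-ratio rule leaves fixed effects open. A reader might infer that the RQ3.1 analysis will use neither list nor score; the documents support only that it pre-specifies neither. This part of the objection stands, and any fix must say how fixed terms sit beside that rule.

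**Adjusted models will be fitted anyway.** RQ3.2 adds scores to models that already contain condition. True, but it does so one score at a time, which yields several adjusted estimates with none designated for the RQ3.1 contrasts.

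**The percentage is soft.** It needs an unstated alpha and a linear model, while the plan expects a count model such as Poisson, with linear or latent basis growth. A two-stage Poisson check gave net ratios of 1.08–1.15 for scores with RQ3.2 power .65–.85, but on assumed inputs (9 words at reading 6, log-slope .25 per reading, SD .12). Latent basis growth was not checked. This limits the precision of the figure, not its direction.

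**The score may disappoint.** Picking the largest past correlation tends to overstate it, and the plan itself expects some predictors to fail. This stands; it is why the weak-score cost belongs beside the gain.

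**Larger gains.** A reader might take .4 to .5 as observed correlations and claim 17–31% net (1/(1 − r²) × 55/56). Observed correlations of that size would imply RQ3.2 power of .89 to .99 in step 1's formula, above the .85 that the plan states.

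**Conclusion.** The point holds as an optional improvement. The RQ3.1 models pre-specify condition as the only between-child term, although a randomised list and potentially useful baseline scores are to hand. One score of the strength implied by the plan's RQ3.2 power is worth about 7–14% more children net in the two treatment-phase models. This assumes two-sided alpha .05, a linear approximation, and a score that performs as planned.

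For the post-treatment models the documents give no correlation with forgetting, so only the list applies there. Its gain is unquantified, and larger than about 1% only if the lists differ clearly.

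A reader might infer that leaving these terms out biases the contrasts or inflates type I error. The documents do not support that: condition is randomised, lists are randomised within it and counterbalanced, and simulated error rates were nominal. Nor would adjustment rescue a contrast whose true power is well below the stated .80.

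**What to change.** 1. **Statistical models, RQ3.1.** Add treated word list and list × time to all four models. In the two treatment-phase models also add one pre-treatment score and score × time. Name the score before outcome data are seen, from the team's earlier studies; if no score has a convincing prior correlation with learning, add list only. Draw the pairwise contrasts from these models.
2. **Inference criteria.** State that these terms are fixed in advance and are not subject to likelihood-ratio selection.
3. **Sensitivity and fallback.** Report the unadjusted contrasts as a sensitivity analysis, and use them if the adjusted count or latent basis model does not converge.
4. **Statistical models, RQ3.2.** State that each predictor is added individually to base models with condition and list but without the chosen score.

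**Cost.** Wording only, no new data; two model degrees of freedom in the post-treatment models and four in the treatment-phase models; separate base models for RQ3.1 and RQ3.2; and about 2–4% of precision if the score proves uninformative.

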### **Hypotheses**

3.1. (a) Lower testing during treatment will lead to steeper positive slopes during treatment than higher testing. The exact pattern of the treatment conditions is not predicted (e.g., low and mid better than high versus low better than mid and high versus low better than mid better than high) (b) Higher testing during treatment will lead to smaller negative slopes (i.e., less forgetting) post-treatment than lower testing. The exact pattern of the treatment conditions is not predicted (e.g., high and mid better than low versus high better than mid and low versus high better than mid better than low). 3.2. (a) Higher language (specifically vocabulary and narrative skills), working memory, and/or episodic learning scores will be associated with steeper positive slopes during treatment. (b) Better treatment learning and/or decay scores will be associated with smaller negative slopes post-treatment, indicating less forgetting. 3.3. (a) Accuracy in predicting learning outcomes will increase at each treatment point, and there will be a point during treatment when outcomes can be accurately predicted. The specific earliest point in treatment (reading 1, 2, 3, 4, or 5) when accurate predictions can be made is unknown without any specific hypothesis. (b) Accuracy in predicting retention outcomes will increase at each post-treatment point, and there will be a point during post-treatment when outcomes can be accurately predicted. The specific earliest point in post-treatment (immediate, 4-week, 8-week) when accurate predictions can be made is unknown without any specific hypothesis.

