#### Transformations

One of the primary dependent variables is a count of the number of words correct which will not fit a normal distribution. Rather than transforming the variable, an appropriate link function such as a Poisson distribution will be used. We will center time at the last intervention reading point for all models.

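### The plan names only Poisson for a words-correct score capped at 30; a binomial model is not excluded but should be specified, because a Poisson log-link analysis would lose treatment-phase power as accuracy rises

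*Combined protocol and SAP*

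**What the plan says.** Under Sampling Plan, Sample size, "definition and naming data will be collected for 30 treated words and 30 control words" for each child. Under Analysis Plan, Statistical models (RQ3.1), the dependent variable is the number of words correct. Because it is unlikely to be normal, "an appropriate link function, such as a Poisson distribution, will be used". Transformations says the same: "an appropriate link function such as a Poisson distribution will be used". Neither section gives a number of trials or a rule for choosing the distribution. Missing data lists Proc MIXED, Proc GLIMMIX and Mplus, so a Gaussian analysis is also possible. For RQ3.3 the plan does treat scores as accuracy: "We will use the accuracy range for the untreated control words to determine the cut-offs for this classification".

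On the estimand, "The slope by treatment condition interaction will be the effect of interest", with no scale stated. The two RQ3.1 hypotheses are that "Lower testing during treatment will lead to steeper positive slopes during treatment than higher testing" and that "Higher testing during treatment will lead to smaller negative slopes (i.e., less forgetting) post-treatment than lower testing". Transformations adds: "We will center time at the last intervention reading point for all models".

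**The concern.** A number correct out of a fixed set of words is a bounded count. A Poisson model has no upper bound. With a log link it reads growth as proportional, so a condition that is learning faster but nearing the ceiling looks less different than it is. The slope-by-condition interaction is the test that answers RQ3.1, so a model that weakens it as children learn works against the study's main question. The weakening depends on a quantity the documents do not give, namely the accuracy children reach by reading 6.

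A second, smaller issue is the scale for forgetting. Hypothesis 3.1(a) predicts that conditions learn at different rates, so they may enter the post-treatment phase at different levels. Whether one condition then forgets more can depend on whether loss is counted in words, in proportion retained or in logits.

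**Working it through.** **Plan's own power figure.** Sample size rationale states .80 or more at d = .5, 20 v 20, 7 points. In closed form, .5 × √(20/2) = 1.58, and Φ(1.58 − 1.96) = .35 two-sided (alpha of .05 assumed; none is stated). If d is in true-slope SDs at reliability .6, then .5 × √.6 × √10 = 1.22, giving .23. The stated .80 is not reproduced. It came from Monte Carlo runs whose population values and definition of d are not given, so this does not show it to be wrong. It is a separate matter.

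**Why the bound matters.** For n = 30, Poisson variance is 30p and binomial variance is 30p(1−p), a ratio of 1/(1−p). Also, d(log p)/d(logit p) = 1−p, so a small logit difference keeps only that fraction on the log scale.

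| Accuracy p | Variance ratio 1/(1−p) | Fraction kept (1−p) |
|---|---|---|
| 10% | 1.11 | .90 |
| 20% | 1.25 | .80 |
| 40% | 1.67 | .60 |
| 60% | 2.50 | .40 |

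**Treatment-phase simulation.** From the plan: 20 v 20, 7 tests, slope reliability .6, ICC .10, time centred at reading 6, likelihood ratio test. Assumed: alpha .05, 5% pre-treatment accuracy, logit-linear growth, the reading-6 accuracies below, and an arm difference of 1.18 slope SD, chosen to give about .80 binomial power. Mixed models with random intercept and slope, Laplace maximum likelihood, 2,000 runs per case (Monte Carlo SE about .01).

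| Mean reading-6 accuracy | Poisson | Binomial | Loss (points) |
|---|---|---|---|
| 10% | .80 | .83 | 3 |
| 20% | .71 | .83 | 12 |
| 35% | .52 | .81 | 29 |
| 40% | .47 | .83 | 36 |
| 50% | .30 | .81 | 51 |
| 60% | .14 | .80 | 66 |

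**Sensitivity.**
- *Smaller effect, .5 slope SD:* .19 v .24 at 20% and .13 v .24 at 40%. Repeat checks put the 40% loss at 11–14 points.
- *Accuracy linear in time, so neither link is true:* .21 v .23 (10%), .27 v .36 (20%), .17 v .37 (35%), .11 v .41 (50%).
- *3% start, reliability .8, 200 runs:* .60 v .75, .39 v .77 and .11 v .75 where a typical child reaches 20, 40 and 60%. With reliability .6: .64 v .81, .31 v .78 and .07 v .76. Group means at the 20% setting were 29% and 26%, which partly explains losses slightly above the first table.
- *Latent basis, 500 runs:* .68 v .80 (20%), .44 v .77 (40%). *ICC .30 at 40%:* .22 v .76.
- *Gaussian slopes, ICC .10, reliability .8:* .76, .80 and .76 at 20, 40 and 60%.
- *Equal arms:* .06 (Poisson) v .05 (binomial). In the 200-run set the binomial test was slightly liberal, at .055–.095.

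**Forgetting scale, arithmetic out of 30.** Falls of 24 to 18 and 12 to 9 both retain 75%. In words they lose 6 and 3. In logits they change by logit(.6) − logit(.8) = −0.98 and logit(.3) − logit(.4) = −0.44.

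Rejection rates (1,000 runs; 20 v 20; immediate test assumed at week 1):

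| Falls compared | Poisson slope | Logit slope | Words lost | Proportion retained |
|---|---|---|---|---|
| 15 to 8 v 15 to 12 (equal starts, real difference) | .82 | .82 | .80 | .84 |
| 24 to 18 v 12 to 9 (equal proportion) | .07 | .53 | .58 | .05 |
| 18 to 13.5 v 12 to 9 (equal proportion) | .06 | .10 | .18 | .07 |
| 18 to 13.5 v 12 to 7.5 (equal words) | .37 | .12 | .07 | .31 |

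Starts of 24 v 12 are 1.79 logits apart. Starts of 18 v 12 are 0.81 apart, close to the 0.87–1.18 logit learning effects used above.

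**The case against.** The strongest reply is that the plan promises an appropriate link and offers Poisson only as an example. An analyst who took that promise seriously could choose a binomial model, and the software listed also allows a Gaussian one, which kept its power at ICC .10. This stands: the defect is an open choice with a poor example, not a planned loss of power. A reader might infer that the plan commits to Poisson or rules out binomial; the wording supports neither.

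The sizes also rest on favourable assumptions. The documents give no expected accuracy, most effects were generated on the scale of the recommended model, and 1.18 slope SD is more than twice a .5-SD reading of the plan's effect. This stands too, and is why the figures are illustrative. The loss does persist when accuracy is linear in time, so it is not only a product of logit-generated data.

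On forgetting, the 24 v 12 example is extreme. With 18 v 12 the logit slope rejects only .10–.12, although the Poisson slope reaches .37 under equal words lost. A reader might infer that one scale gives a false verdict on 3.1(b). That would presuppose which scale is right. No scale is neutral and the documents choose none, so a rejection in words lost is correct if words lost is the intended measure.

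Finally, the attachments on manipulated and measured variables are not available here. If fewer than 30 words are tested on some occasions, a fixed denominator of 30 would be wrong.

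**Conclusion.** The point holds in conditional form. The plan leaves the distribution open and names one that does not suit a score bounded by the words tested. If Poisson with a log link is used, treatment-phase power falls as accuracy rises: little at 10% reading-6 accuracy, about 10–15 points at 20%, roughly 25 to 40 or more at 35–40%, and most of it from 50–60%. These figures assume 20 v 20, reliability .6, ICC .10, logit-scale effects set to about .80 binomial power, and accuracies not found in the documents. At .5 slope SD the loss is about 5 points at 20% and 11–14 at 40%.

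Three stronger readings are not supported. Type I error with equal arms is not materially inflated. The loss is specific to the Poisson log-link model and was not seen with a Gaussian model at ICC .10. Specifying a binomial model does not establish the stated .80 at d = .5.

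The forgetting scale is a secondary gap. It matters little with equal starts. With unequal starts, the conclusion on 3.1(b) can depend on a scale not yet named, though the effect is mostly modest at a gap such as 18 v 12 words. This is a cheap improvement that should be made.

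**What to change.** In Statistical models and in Transformations, replace the Poisson example with wording such as:

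> Number correct out of the number of words tested at that occasion (30 where all words are tested) will be modelled as binomial with a logit link and child random intercept and slope, with a beta-binomial model or observation-level random effect if over-dispersed, fitted by Laplace or quadrature maximum likelihood.

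Naming the estimation method makes the maximum likelihood commitment under Missing data explicit and supports the likelihood ratio tests under Inference criteria.

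For hypothesis 3.1(b), the sponsor should name the scale of comparison before outcomes are seen, for example words lost or proportion retained, and report each condition's reading-6 mean and fitted word counts at every test. If the measure is anchored at reading 6, the plan should note that Study design has those data collected by the treating assistant, who knows the condition, although scoring is blind.

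Cost: plan wording and model code, with no new data. Effects become odds ratios that must be back-transformed to words, and fitting takes somewhat more work. The sponsor should confirm that the chosen software fits a latent basis version. Large-sample tests of words lost and proportion retained ran at .05–.08 under their own nulls with 20 per arm, so a bootstrap or t reference is advisable if either is used.
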